Considering these difficulties, various adjunctive treatments have been investigated to supplement Scaling and Root Planing as local delivery drugs. These include systemic and localized delivery of antibiotics (Clarithromycin gel, minocycline microspheres), chlorohexidine, bisphosphonates, statins & photodynamic therapy to reduce bacterial counts and improve clinical periodontal parameters such as probing depth reduction, gaining clinical attachment level and bone defect (BD) fill in periodontitis (**Zandbergen et al., 2013**), (**Akram et al., 2016**), (**Abduljabbar et al., 2017**).

Metformin a biguanide used in treatment of diabetes mellitus type II as an oral hypoglycemic drug, has shown stimulating effect on osteoblastic lineages leading to osteoblast differentiation and bone formation. MF increased type-I collagen production in both osteoblast-like cell lines and stimulated alkaline phosphate activity in MC3T3E1 osteoblasts (**Cortizo et al., 2005**). Since MF benefits on fracture reduction and takes positive action on osteoblasts, it appears possible that this agent may have protective effects on bone loss. Recent in vivo and in vitro studies suggest that metformin reduces receptor activator for nuclear factor-kappa B ligand (RANKL) and stimulates osteoprotegerin (OPG) expression in osteoblasts, further inhibits osteoclast differentiation and prevents bone loss in ovariectomized rats (**Mai et al., 2011**). In another study on ligature-induced periodontitis, the MF treatment of rats induced a significant reduction in alveolar bone loss compared to vehicle-treated rats (**Bak et al., 2010**).

Randomized clinical trials regarding the use of Locally delivered metformin in periodontitis, The 1% MF gel used along with Scaling and Root Planing was found to provide improvement in clinical and radiographical parameters confirmed by Studies done by (**Rao et al., 2013**) & (**Pradeep et al., 2017**) in the form of significant increase in the PD reduction, CAL gain, and improved IBD depth reduction in vertical bone defects. So In this study we will evaluate The 1% MF gel along with SRP was found to provide improvement in clinical and radiological parameters

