confirmed by Studies done by (**Rao et al., 2013**) & (**Pradeep et al., 2017**) in the form of significant increase in the PD reduction, CAL gain, and improved IBD depth reduction in vertical bone defects. So In this study we will evaluate the effect of the locally delivered metformin in the form of clinical and biochemical assessment.

Aim of Study

Primary outcome :

To evaluate the clinical parameters before & after the application of locally delivered metformin as an adjunctive therapy to non surgical periodontal treatment of Stage III periodontitis.

Secondary outcome :

To measure the RANKL and OPG levels in GCF before & after application of metformin as an adjunctive therapy to non surgical periodontal treatment of Stage III periodontitis.

Subjects and Methods

Study design and Sample size calculation :

In this randomized controlled study, total sample size of 16 patients (8 patient/group) were selected for this study. The sample size was calculated to yield a 95% power in the results of this study based on the results of a previous study (Pradeep et.al., 2017) in which the authors found a significant difference in IBD depth between test and placebo groups (effect size=.2.08 mm, alpha (2 tailed)=.05). The number will be increased to 20 in each group to compensate for dropouts.

Patient Selection :

Forty patients, having periodontitis, will participate in this randomized clinical study. The subjects will be recruited consecutively from the outpatient clinic of Oral Medicine, Periodontology, oral Diagnosis and Radiology Department, Faculty of Dentistry, Ain Shams University. The purpose of the study will be explained to all patients and an informed consent will be signed before the conduction of the study. The proposal will be presented to the faculty of Dentistry Ain Shams University Research Ethics committee and have to be approved before starting the research

Inclusion Criteria will be :

1. Patients with Stage III & IV Periodontitis.
2. Age range (30 - 50) years.
3. Good compliance with the plaque control instructions following initial therapy.
4. Availability for follow up and maintenance program.

Exclusion Criteria will be :

1. Smokers
2. Systemic diseases which could influence the outcome of the therapy (According to Cornell Medical Index-Health Questionnaire).
3. Pregnant and lactating females.
4. Vulnerable groups of patients' e.g (prisoners, handicapped patients and decisionally impaired individuals).

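### The only power claim (95%, 8 per group) comes from intrabony defect depth, a measure this trial does not define; no power is documented for PI, GI, PD or CAL

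*Combined protocol and SAP*

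**What the plan says.** Under Study design and Sample size calculation, the protocol sets 16 patients, 8 per group, and states: "The sample size was calculated to yield a 95% power in the results of this study". The effect behind this is from a cited earlier trial, where "the authors found a significant difference in IBD depth between test and placebo groups (effect size=.2.08 mm, alpha (2 tailed)=.05". No SD is given. The paragraph ends: "The number will be increased to 20 in each group to compensate for dropouts".

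The primary outcome, under Aim of Study, is "To evaluate the clinical parameters before & after the application of locally delivered metformin", with no single parameter named. The list of clinical evaluation parameters contains PI, GI, PD, CAL and, as item e, a standardised periapical radiograph, all at baseline and 6 months. Under Outcomes Assessment, clinical assessment is described with a graduated probe only. The disease criterion for inclusion is "Patients with Stage III & IV Periodontitis". Statistical Analysis names no test.

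IBD depth appears only in the sample size sentence and in the literature review, which reports from earlier trials a "significant increase in the PD reduction, CAL gain, and improved IBD depth reduction in vertical bone defects".

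**The concern.** A power figure belongs to one endpoint, one effect and one SD. Here it is attached to the study's results in general, while its source is a bone measurement that the trial never says how to take. The trial also does not restrict entry to patients who have the defect being measured.

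As written, a null result on probing depth or attachment level could be reported as coming from a trial with 95% power, although the plan documents no power for either. A reader also cannot tell what attrition is expected or why 20 per group was chosen.

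**Working it through.** **Inputs from the sample size paragraph:** effect 2.08 (printed with a stray leading point and the unit mm), two-sided alpha 0.05, power 95%, 8 per group, raised to 20. **Assumed, because not stated:** one value per patient, unadjusted two-sample t test, equal groups.

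**Formula.** With n per group and standardised difference d, power is the probability that a noncentral t variable with 2n − 2 degrees of freedom and noncentrality d × √(n/2) exceeds the two-sided 5% critical value in absolute size.

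**Step 1: reproduce the plan's figure, taking 2.08 as standardised.**
- n = 7: noncentrality 2.08 × √3.5 = 3.89, power 94.6%.
- n = 8: noncentrality 2.08 × √4 = 4.16, power 97.1%.

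So 8 is the smallest group size reaching 95%, and the arithmetic is sound on this reading. Reading the stray point as 0.208 would need about 601 per group (normal approximation), so that is not what was meant.

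**Step 2: take 2.08 as millimetres, as printed.** The standardised difference detectable with 95% power is 2.103 at n = 7 and 1.941 at n = 8.
- Largest SD giving 95% at 8 per group: 2.08 / 1.941 = 1.07 mm.
- Largest SD giving 95% at 7 per group: 2.08 / 2.103 = 0.99 mm.

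Eight is therefore the minimum size only for an SD between about 0.99 and 1.07 mm. For assumed SDs of 1.25, 1.5 and 2 mm, power at 8 per group would be 87%, 73% and 49%. At 20 per group the limit relaxes to 2.08 / 1.170 = 1.78 mm. The unit is either wrong or lacks its SD.

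**Step 3: what the planned size delivers for any single endpoint.**

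| Evaluable per group | d at 80% power | d at 95% power |
|---|---|---|
| 20 | 0.91 | 1.17 |
| 18 (assumed) | 0.96 | 1.24 |
| 16 (assumed) | 1.02 | 1.32 |

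Conversely, 20 per group gives 34% power for an assumed d of 0.5, 69% for 0.8 and 87% for 1.0. These effects are illustrative, since the documents give none for PI, GI, PD or CAL.

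Baseline adjustment would help. Multiplying by √(1 − r²) for an assumed baseline correlation r of 0.3, 0.5 or 0.7 lowers the 20-per-group figures to 0.87, 0.79 or 0.65 (80% power) and 1.12, 1.01 or 0.84 (95% power).

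**Step 4: the dropout sentence.** Going from 8 to 20 implies a loss of 1 − 8/20 = 60%, a rate stated nowhere. Keeping 8 completers with 10%, 20%, 30%, 40% or 50% dropout needs 8/(1 − rate), rounded up: 9, 10, 12, 14 or 16 per group.

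**The case against.** The strongest reply is that the radiograph is item e in the protocol's own list of clinical evaluation parameters, at baseline and 6 months, so a bone measure belongs to the primary set and only the reading method was left out. The literature review supports this once, saying that adjunctive treatments "improve clinical periodontal parameters such as probing depth reduction, gaining clinical attachment level and bone defect (BD) fill in periodontitis". Elsewhere it separates the two kinds of measure, saying the gel "was found to provide improvement in clinical and radiographical parameters". The sponsor may well have intended to measure IBD depth. Even so, the 95% would apply to one item of the five listed, and only in patients who have such a defect. It would say nothing about the four probe- and index-based parameters.

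It can also be said that the paragraph openly discloses its basis and never claims 95% for PD or CAL by name. That is true, but the claim is worded for the study's results without limit, and the primary outcome names no endpoint that would narrow it.

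Third, the millimetre question matters less at the planned 20 per group, where an SD up to about 1.78 mm still gives 95%. This stands. The unit and the dropout sentence are minor points, and the extra patients do no harm to power.

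Finally, if the adequacy of 20 per group is undocumented, 40 patients cannot be endorsed either. That is also right: keeping 40 while stating what it delivers is an honest description of the size, not a finding that it suffices.

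**Conclusion.** The concern holds. The calculation behind 8 per group is not an arithmetic error if 2.08 is standardised. The fault is that its 95% is claimed for the whole study when the only supporting effect belongs to a measure the protocol does not define and for which it does not select patients. For PI, GI, PD and CAL no power can be computed from the documents.

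Under the assumptions above, 95% power at 20 per group requires a standardised difference of at least 1.17, and 80% requires 0.91. The documents do not show that 20 per group is too few; they leave it unsupported. The design survives, but the stated justification should be corrected.

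**What to change.** 1. Remove the 95% as a property of the study's results. Alternatively, confine it to IBD depth, define that measurement from the periapical radiograph, and state how many patients are expected to have such a defect. On the plan's own effect, taken as standardised, at least 8 of the 20 in each group would need a measurable defect and a 6-month reading.
2. Name one primary clinical endpoint, for example 6-month PD or CAL at the treated sites, with one summary value per patient.
3. State what the size delivers. Suggested text: With 20 per group, one value per patient, an unadjusted two-sample t test and two-sided alpha 0.05, the trial has 80% power for a standardised difference of 0.91 and 95% for 1.17; with an assumed 16 evaluable per group, 1.02 and 1.32. Add the endpoint's SD and its source so that this can be read in mm, judge whether the detectable difference is realistic, and recompute if the chosen analysis differs, for example if it adjusts for baseline.
4. Label 2.08 as standardised, or give its SD.
5. Replace the dropout sentence with the expected attrition and the actual reason for 20 per group.

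The 40 patients, eligibility, treatment and visits can stay as they are. This is more than rewording: naming a primary endpoint makes the other clinical parameters secondary, so it should be done before any outcome data are compared by group. The stated power becomes less favourable, and keeping the IBD claim requires a defined reading of radiographs already planned.
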